7.3.2 Serious adverse event reporting by Investigators

Adverse events classified by the treating investigator as **serious** require expeditious handling and reporting to sponsor in order to comply with regulatory requirements. Serious adverse events may occur at any time from the signing of the informed consent form through the 30-day follow-up period after the last dose of study drug. Sponsor/sponsor representative must be notified of all SAEs, regardless of causality, within 1 day of the first knowledge of the event by the investigator. The SAE report should be sent to the sponsor/sponsor representative **via e-mail**. Follow-up

information for SAEs and information on non-serious AEs that become serious should also be reported to Sponsor as soon as it is available. Investigators must report SAEs and follow-up information to their responsible IRB/IEC according to the policies of the responsible IRB/IEC.

7.3.3 Sponsor SAE Reporting Requirements

Sponsor/Sponsor representative is responsible for reporting relevant SAEs to the competent authority, other applicable regulatory authorities, and participating investigators, in accordance with ICH guidelines, FDA regulations, and/or local regulatory requirements.

Sponsor/sponsor representative is responsible for reporting unexpected fatal or life-threatening events associated with the use of the trial drugs to the regulatory agencies and competent authorities via fax/mail within 7 calendar days after being notified of the event.

The Sponsor will report all related, unexpected SAEs, including non-death/non-life-threatening related unexpected SAEs associated with the use of the trial medications to the FDA by a written safety report within 15 calendar days of notification. Reporting to the IRB/IEC will be done according to institutional policy.

7.3.4 Pregnancy, Abortion, Birth Defects/Congenital Anomalies

Pregnancy, abortion, birth defects, and congenital anomalies are events of special interest. Please refer to pregnancy section 7.4.1 for specific instructions.

7.4 Protocol-Defined Events of Special Interest

The following are events of special interest and will need to be reported expeditiously.

7.4.1 Pregnancy, Abortion, Birth Defects/Congenital Anomalies

Female patients of child-bearing potential (see Appendix A) must consent to use two medically acceptable method of contraception throughout the study period and for 4 weeks after the last dose of Tenalisib.

During the course of the trial, all female patients of childbearing potential and pregnant partner of male subjects must contact the treating investigator immediately if they suspect that they may be pregnant (a missed or late menstrual period should be reported to the treating investigator).

If an investigator suspects that a patient may be pregnant after the patient has been receiving trial drug(s), the trial drug(s) must immediately be withheld until the result of the pregnancy test is confirmed. If a pregnancy is confirmed, the trial drug(s) must be immediately and permanently stopped, the patient must be discontinued from the trial, and the investigator must notify the medical monitor and Sponsor Representative as soon as possible. If a patient becomes pregnant while enrolled in the trial, a Pregnancy Form should be completed and mailed to the Sponsor. The outcome of the pregnancy will be monitored as outlined in Appendix A.

Congenital anomalies/birth defects always meet SAE criteria, and should therefore be expeditiously reported as an SAE, using the previously described process for SAE reporting. A Pregnancy Form should also have been previously completed and will need to be updated to reflect the outcome of the pregnancy.

7.4.2 Overdose

An overdose is defined as accidental or intentional administration of any dose of product that is considered both excessive and medically important. For purposes of this trial, an overdose will be defined as any dose exceeding the proposed dose of Tenalisib (e.g. > 800 mg twice a day).

Symptomatic and non-symptomatic overdose must be recorded in the CRF. Any accidental or intentional overdose with the trial treatment that is symptomatic, and if not fulfilling a seriousness criterion, is to be reported to the Sponsor immediately as an AE. All symptomatic overdose, fulfilling a seriousness criterion is to be reported as an SAE as per the SAE reporting procedure. For patients who experience overdose, treatment should consist of supportive therapy. A decision to interrupt treatment or dose reduction to be taken depending on the symptoms.

7.5 Dose Modifications

The dose modification should be performed for the drug toxicity or underlying disease conditions. Guidelines (Refer [Table 2](#) and [3](#)) are intended to be applied when the investigator determines the event related to Tenalisib. Please note the dose modifications provided below should be used as a guidance and should be determined as per PI's clinical judgement.

Patients may resume Tenalisib, provided that the toxicity has resolved to Grade ≤ 2 or baseline and there is no clinical or radiographic evidence of disease progression. If study drug is delayed > 2 weeks because of an adverse event, strategy of re-initiation of study drug should be discussed with medical monitor.

At the discretion of the Investigator, a dose re-escalation may be permitted for patients who previously had a dose reduction. Holidays from study drug are discouraged. Any patient in whom similar toxicity recurs at the reduced dose should be discontinued from further Tenalisib treatment. Note: In exceptional case, a patient may be allowed following a careful assessment of benefit and risk by the investigator and with approval from the medical monitor.

Table 2: Dose Modifications for Hematologic Toxicity

Worst CTCAE Grade Toxicity	Action to be Taken
HEMATOLOGIC	
Neutropenia (ANC)	
Grade 3 $1.0 \times 10^9 / L < ANC \geq 0.5 \times 10^9 / L$	Maintain dose level. Monitor ANC at least weekly.
Grade 4 $0.5 \times 10^9 / L < ANC$	First incidence: Withhold* dose until resolved to \leq Grade 2 or baseline. Monitor ANC at least weekly. Resume treatment at the same dose level. Subsequent occurrence: Hold dose until resolved to \leq Grade 2 or baseline. Consider growth factor support. Resume treatment at the reduced dose level (Tenalisib 400 mg BID) if warranted.
Grade 3 Febrile neutropenia $ANC < 1000 / mm^3$ with a single temperature of $> 38.3^{\circ}C (101^{\circ}F)$	Withhold* dose until resolved to \leq Grade 2 or baseline, consider growth factor support, then reduce by 1 dose level (Tenalisib 400 mg BID), if

or a sustained temperature of $\geq 38^{\circ}\text{C}$ (100.4°F) for more than one hour.	warranted. If the ANC is $<1 \times 10^9/\text{L}$ ($1000/\mu\text{L}$) before therapy, the dose shall not be modified as long as $\text{ANC} > 0.5 \times 10^9/\text{L}$.
Thrombocytopenia	
Grade 3 thrombocytopenia with Grade 1 bleeding	Maintain Tenalisib dose. Monitor platelet count at least weekly.
Grade 3 thrombocytopenia with Grade 2 bleeding OR Grade 4 thrombocytopenia ($20.0 \times 10^9/\text{L} < \text{PLT}$)	1st occurrence: Withhold** dose until to \leq Grade 2 or baseline or resolution of bleeding. Consider platelet transfusion as necessary. Resume treatment at the same dose level. Subsequent Occurrences: Withhold dose until to \leq Grade 2 or baseline or resolution of bleeding. Consider platelet transfusion as necessary. Resume treatment at the reduced dose level (Tenalisib 400 mg BID) if warranted. Doses should not be modified if Grade 4 thrombocytopenia is present at baseline.

* The treatment should be permanently discontinued if withhold of study drug due to drug related toxicity is for > 28 days unless approved by medical monitor.

** Patient receiving concomitant medication (e.g. anti-platelets, aspirin, or low molecular weight heparin) should be discussed with the medical monitor for further management.

Table 3: Dose Modifications for Non-Hematologic Toxicities

NON-HEMATOLOGIC	Action to be Taken
Hepatic*	
Transaminitis
 
Grade 1-2 Transaminitis (ALT/AST $>1-3 \times \text{ULN}$ if baseline is normal; $1.5 - 3 \times \text{baseline}$ if baseline is abnormal):
 
 Maintain Tenalisib dose and initiate prednisone 40 mg daily. Monitor AST/ALT weekly until resolved and then taper steroid. Withhold Tenalisib in case of development of grade 2 transaminitis or worsening of Grade 1 transaminitis while on steroids. 
Grade 3 Transaminitis ($\text{ALT/AST} >5-20 \times \text{ULN}$; $>5-20 \times \text{baseline}$ if baseline is abnormal):
 
 Withhold Tenalisib and monitor ALT/AST twice a weekly until Grade ≤ 1; restart Tenalisib at one dose lower (Tenalisib 400 mg BID). Initiate prednisone 1 mg/kg in case no improvement after withholding Tenalisib for 1 week. Monitor ALT/AST twice a weekly until Grade ≤ 1; restart Tenalisib at one dose lower (Tenalisib 400 mg BID). and taper steroid. If no immediate response to steroids within 7 days, initiate mycophenolate mofetil. In case of recurrence of transaminitis at reduced doses, discontinue Tenalisib permanently after assessing risk versus benefit. 
Grade 4 Transaminitis ($\text{ALT/AST} >20 \times \text{ULN}$; $>20 \times \text{baseline}$ if baseline is abnormal):
 
 Tenalisib should be permanently discontinued. 
Bilirubin:
 
 Grade 2 ($> 1.5-3 \times \text{ULN}$; $>1.5- 3 \times \text{baseline}$ if baseline is abnormal): Maintain Tenalisib dose. Monitor at least weekly until $\leq 1 \times \text{ULN}$

	
 • Grade 3 ($> 3-10 \times \text{ULN}$; $> 3 - 10 \times \text{baseline}$ if baseline is abnormal): Withhold Tenalisib. Monitor at least weekly until bilirubin is $\leq 1 \times \text{ULN}$; Restart Tenalisib at one dose lower (Tenalisib 400 mg BID). • Grade 4 ($> 10 \times \text{ULN}$; $> 10 \times \text{baseline}$ if baseline is abnormal): Discontinue Tenalisib permanently
Infection	
Grade 3 or higher sepsis or pneumonia
 
 • Withhold Tenalisib until infection has resolved. • Restart at the same or at the reduced dose (Tenalisib 400 mg BID)
Skin rash (Cutaneous reactions)	
Grade 1-2
 
 • Maintain Tenalisib dose. Initiate supportive care with emollients, antihistamines (for pruritus), or topical steroids • Monitor closely until resolved. 
Grade 3
 
 • Withhold Tenalisib dose. Initiate supportive care with emollients, antihistamines (for pruritus), or topical steroids • Monitor at least weekly until resolved. • Restart Tenalisib at the reduced dose level (Tenalisib 400 mg BID). • If severe cutaneous reaction does not improve, worsens, or recurs, discontinue Tenalisib 
Life threatening or SJS, TEN, DRESS (any grade)
 
 • Discontinue Tenalisib permanently.
Pneumonitis without suspected infectious cause	
Moderate (Grade 2) symptomatic pneumonitis
 
 • Withhold Tenalisib dose. Initiate systemic steroid therapy. If pneumonitis recovers to Grade 0 or 1, Tenalisib may be resumed at reduced dose. • If non-infectious pneumonitis recurs or patient does not respond to steroid therapy, discontinue Tenalisib. 
Severe (Grade 3) or life-threatening pneumonitis
 
Discontinue Tenalisib. Treat with systemic steroid therapy.

Non-infectious Diarrhea	
Moderate diarrhea and responsive to antidiarrheal agents:
 
 • Maintain Tenalisib dose. Monitor at least weekly until resolved. 
Moderate diarrhea and unresponsive to antidiarrheal agents:
 
 • Withhold Tenalisib dose. Initiate supportive therapy with enteric acting steroids (e.g., budesonide). • Monitor at least weekly until resolved. • Restart Tenalisib at the reduced dose level (Tenalisib 400 mg BID). 
Severe diarrhea or hospitalization
 
 • Withhold Tenalisib dose. Initiate supportive therapy with enteric acting steroids (e.g., budesonide) or systemic steroids. • Monitor at least weekly until resolved. • Restart Tenalisib at the reduced dose level (Tenalisib 400 mg BID). 
Life threatening diarrhoea
 
 • Discontinue Tenalisib permanently. •
Cardiac	If a QTcF > 500 msec has been demonstrated, hold dose.

	
The patient will be closely monitored until the QTcF <500 msec and the QTcF has returned to <30 msec from baseline. Immediate attention to potassium and magnesium and other clinical factors such as oxygenation and ischemia should be addressed.
 
All cardiac events should be treated as per the local standard of care and referral to a specialist if clinically indicated. Any final decisions concerning dose modifications or permanently discontinuing the patient from study drug due to QTcF prolongation will occur after discussion with medical monitor.

OTHER NON-HEMATOLOGIC	Action to be Taken
Grade 1 or 2	None
Grade 3	Withhold Tenalisib dose until toxicity Grade ≤ 2 . Restart Tenalisib at one dose lower (Tenalisib 400 mg BID) if warranted.
Recurrence of grade 3 toxicity	Withhold Tenalisib dose until toxicity Grade ≤ 2 ; Restart Tenalisib at one dose lower or discontinue treatment
Grade 4	Withhold Tenalisib dose until toxicity Grade ≤ 2 ; Restart Tenalisib at one dose lower (Tenalisib 400 mg BID) or discontinue Tenalisib
Recurrence of grade 4 toxicity	Discontinue Tenalisib

*The treatment should be permanently discontinued if withhold of study drug due to drug related toxicity is for > 28-days unless approved by medical monitor.

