3.4.5 Precautions and Risks associated with Investigational Product

- Monitoring of liver enzymes and levels of TSH, T3, and T4 in subjects receiving Tenalisib is recommended based on target organ toxicity. Patients should be monitored for increased ALT/AST, skin rash/drug reaction, neutropenia as these events are reported with Tenalisib. Monitor patients for signs and symptoms of these events and interrupt Tenalisib for Grade 3 or higher event. In addition, enteritis (colitis), pneumonia/pneumonitis as these events are reported with other PI3K inhibitors.
- Tenalisib may cause serious infections that may include sepsis and other infections. Monitor patients for signs and symptoms of infection and interrupt Tenalisib for Grade 3 or higher infection.
- Tenalisib elicits no photo instability upon exposure to ultraviolet (UV) radiations. However, in absence of in vitro data, possibility of photo-toxicity with Tenalisib cannot be ruled out.
- Tenalisib demonstrated moderate to high inhibition of CYP3A4 enzymes. Therefore, concomitant administration of Tenalisib with CYP3A4 substrates (e.g. calcium channel blockers, warfarin, carbamazepine, macrolide antibiotics, lovastatin, simvastatin, terfenadine) may reduce clearance of these drugs increasing the risk of adverse events.
- Similarly, as Tenalisib is inhibited by CYP3A4/5 and CYP2C9, there is possibility of drug interaction with inhibitors or inducers of CYP3A4 and CYP2C9. If concomitant treatment of these drugs is clinically warranted, careful observation of the patient is advised. Raised INR has been reported with concomitant warfarin administration. Therefore, use of heparin or warfarin is generally avoided. Low molecular weight heparin (LMWH) is advised for prophylaxis and treatment of venous thrombosis.
- Strong inhibitor or inducers should be avoided as directed in Section on prohibited medication. Please refer to the recent Investigator Brochure for additional safety information.
- In absence of reproductive toxicity and genotoxicity data, the study participants should be advised to follow post treatment contraceptive measures.

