7.2 Adverse Event/Serious Adverse Event Causality Assessment

The causality assessment will be categorized as related and not related.

- **Related:** All toxicities should be considered to be related to Tenalisib unless there is a clear alternative explanation.
- **Not related:** If there is no temporal association, or another etiology has been identified as the cause, or the trial treatment cannot be implicated based upon the current information.

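### Section 3.4.5 says to interrupt Tenalisib at Grade 3 neutropenia, Table 2 says to keep the dose unchanged when there is no fever, and nothing in the protocol says which prevails

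*Combined protocol and SAP*

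**What the plan says.** Protocol Section 3.4.5 (precautions) says: "Patients should be monitored for increased ALT/AST, skin rash/drug reaction, neutropenia as these events are reported with Tenalisib". The next sentence reads: "Monitor patients for signs and symptoms of these events and interrupt Tenalisib for Grade 3 or higher event". It makes no exception for absence of fever, for the count before therapy or for causality. The section points onward to the prohibited-medication section and the Investigator's Brochure, not to Section 7.5.

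Protocol Section 7.5, Table 2, has three neutropenia rows. For Grade 3 the action is: "Maintain dose level. Monitor ANC at least weekly". For Grade 4 the dose is withheld. For Grade 3 febrile neutropenia it is withheld and then reduced if warranted. The febrile row also holds a sentence on low baseline counts: if the ANC is below 1 × 10⁹/L "before therapy, the dose shall not be modified as long as" the ANC stays above 0.5 × 10⁹/L.

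On the standing of the tables, Section 7.5 says they are "intended to be applied when the investigator determines the event related to Tenalisib" and that the "dose modifications provided below should be used as a guidance and should be determined as per" the PI's clinical judgement. It does not mention Section 3.4.5. On causality, Section 7.2 says: "All toxicities should be considered to be related to Tenalisib unless there is a clear alternative explanation".

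**The concern.** Neutropenia is one of the few events the protocol names as reported with Tenalisib, and safety and tolerability is the first objective. Two sites that both follow the text could manage the same patient in opposite ways.

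The choice has consequences further on. A site that interrupts falls under the general condition for resuming and, after a delay of more than 2 weeks, under the discussion with the medical monitor. It may also reach the Table 2 footnote on permanent discontinuation after more than 28 days of withholding, which the medical monitor can waive. That footnote is worded generally, but its asterisk stands on the Grade 4 and febrile rows and not on the Grade 3 row. A site that keeps dosing meets none of these rules. A monitor recording deviations under Section 11.2 has no single standard against which to judge either site.

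**Working it through.** There is no figure in the plan to reproduce. The check sets the two instructions side by side, case by case.

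| Case | Section 3.4.5 | Section 7.5, Table 2 | Result |
|---|---|---|---|
| Grade 3, no fever, judged related | interrupt | maintain | opposite |
| Grade 3 with fever, ANC before therapy not below 1.0 | interrupt | withhold | agree |
| Grade 4 | interrupt | withhold | agree |
| ANC before therapy below 1.0, current ANC above 0.5 and below 1.0 | interrupt | dose not modified | opposite if *modified* includes withholding |
| Grade 3, judged not related | interrupt | not intended to apply | only 3.4.5 speaks |

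(ANC in 10⁹/L.)

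**Is Section 3.4.5 only loose background?** Its other Grade 3 instructions match Table 3. Transaminitis and rash are withheld at Grade 3, and sepsis or pneumonia at Grade 3 or higher. Among these events, the opposite instruction was found only for neutropenia.

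**Does relatedness separate the two?** Table 2 applies to events judged related. Under Section 7.2 a toxicity counts as related unless there is a clear alternative explanation, so a Grade 3 neutropenia without one falls under both instructions. If relatedness were the intended divide, the literal result would be to interrupt for unrelated neutropenia and to maintain for related neutropenia. That is not a plausible reading.

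**How much of Grade 3 is affected?** Inputs: the cut points 1.0 and 0.5 × 10⁹/L in Table 2, and the assumption that lower counts are worse. Grade 3 is then 0.5 ≤ ANC < 1.0. The maintain row covers all of it when there is no fever. The low-baseline sentence covers 0.5 < ANC < 1.0, which is the same range without the single value 0.5.

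**Does *modified* include withholding?** The term is not defined. Withholding is, however, listed under the table title "Dose Modifications for Hematologic Toxicity", so the sentence can be read as an instruction not to withhold. On that reading it conflicts with Section 3.4.5 even if it is confined to the febrile row, and it also conflicts with that row's own withhold instruction.

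**Source-page check (secondary).** In the machine-read text the Grade 3 line is 1.0 < ANC ≥ 0.5, which reduces to ANC > 1.0. The Grade 4 line is 0.5 < ANC, and the Grade 4 platelet line is 20.0 < PLT (× 10⁹/L). As read, these contradict their grade labels. The febrile row uses ANC < 1000/mm³, and 1000/mm³ × 10⁶ mm³/L = 1.0 × 10⁹/L, which supports 1.0 as the upper limit of Grade 3. The signs may be faults of text extraction. The main conflict rests on the printed Grade 3 label and not on them.

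**The case against.** The strongest reply is that Section 3.4.5 is a general list of precautions, while Section 7.5 is the dedicated dose-modification section with a row for each event. A reader may naturally let the specific override the general. The tables are guidance under the PI's judgement, so differences between sites are already allowed, and a medical monitor is available for questions (Section 12.3). This softens the conflict but does not resolve it. The protocol states no rule that the specific prevails. The guidance sentence allows departure from the tables and leaves Section 3.4.5 unqualified.

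A second reply concerns scope. The not-related definition in Section 7.2 also covers cases where the drug cannot be implicated on current information, and some patients may continue a combination agent. Events judged not related give no conflict. That stands: the direct contradiction is limited to events treated as related, which is the default.

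A third reply concerns reach. Blood counts are done only as standard of care at the investigator's discretion, and entrants have already completed at least 6 cycles. Non-febrile neutropenia would mostly come to light through a count ordered at discretion. This bears on how often the conflict arises, not on whether it exists.

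Finally, the low-baseline point depends on an undefined word, and it is uncertain whether the sentence applies outside its row. It is therefore stated here only as a possible conflict.

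**Conclusion.** The concern holds. For non-febrile Grade 3 neutropenia treated as related to Tenalisib, the protocol gives two opposite dosing instructions and no means of choosing between them. The conflict covers every ANC in Grade 3 (0.5 ≤ ANC < 1.0 × 10⁹/L, assuming the table's cut points with lower counts worse). The low-baseline sentence adds a probable but conditional second conflict over the same range apart from 0.5.

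The number of patients affected cannot be derived from the documents. The SAP plans no analysis of interruptions, so any effect on its adverse event summaries is indirect and not quantified. The case for correction rests on patient safety and consistent conduct. Confidence is high for the conflict between Sections 3.4.5 and 7.5. Nothing in this conclusion depends on the inequality signs, and it takes no view on which instruction is clinically right.

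**What to change.** 1. Reconcile Section 3.4.5 with Table 2, including the low-baseline sentence, so that one action is stated for each case, or state which section prevails. The clinical team decides which.
2. State whether the low-baseline sentence applies only to the febrile row, and whether *modified* includes withholding.
3. Check the Grade 3 ANC, Grade 4 ANC and Grade 4 platelet inequalities against the source page. If they are printed as read, make the ranges agree with their grade labels.

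Investigator judgement under Section 7.5 would still allow some variation, but from a single written starting instruction.

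The cost is a short amendment: one bullet in Section 3.4.5 or the affected Table 2 cells, plus up to three corrected inequalities. Section 11.1 requires IRB/IEC submission and approval, although Section 10.1 provides for notification only for some amendments. Regulatory approval is needed if required (Section 10.2), and site training as necessary (Section 10.6.3). Under Section 10.5, re-consent arises only if the change is judged to alter the trial design or the risks to patients substantially. Data collection does not change.

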7.1.2 Recording of adverse events

All adverse events should be graded as per the CTCAE v5.0. and should be recorded in the case report form. All adverse events resulting in discontinuation from the trial should be followed until resolution or stabilization. Patients must be followed for AEs for 30 calendar days after the last dose of study treatment or till new anti-cancer treatment is initiated whichever is earlier. All new AEs occurring during this period must be reported and followed until resolution unless, in the opinion of the investigator, the adverse event or laboratory abnormality/ies are not likely to improve because of the underlying disease. After 30 days of completion of protocol-specific

treatment or discontinuation, only AEs, SAEs, or deaths assessed by the investigator as treatment related are to be reported.

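### Table 2 prints three blood-count limits with the inequality reversed: Grade 4 neutropenia, the upper bound of Grade 3 neutropenia, and Grade 4 thrombocytopenia

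*Combined protocol and SAP*

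**What the plan says.** Protocol section 7.5, Table 2 (hematologic toxicity) pairs a grade and a count limit with a dosing action.

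- Grade 3 neutropenia: "Grade 3 $1.0 \times 10^9 / L < ANC \geq 0.5 \times 10^9 / L". Action: keep the dose and check ANC at least weekly.
- Grade 4 neutropenia: "Grade 4 $0.5 \times 10^9 / L < ANC". Action: withhold; after a recurrence, consider growth factor and resume at a reduced dose if warranted.
- Thrombocytopenia: the withhold row covers Grade 3 with Grade 2 bleeding (no numeric limit) or "Grade 4 thrombocytopenia ($20.0 \times 10^9/\text{L} < \text{PLT". Action: withhold and consider platelet transfusion.
- Febrile neutropenia: "Grade 3 Febrile neutropenia $ANC < 1000 / mm^3" with fever. Action: withhold. For patients whose ANC was below 1 ×10⁹/L before therapy, the row adds that "the dose shall not be modified as long as $\text{ANC} > 0.5 \times 10^9/\text{L".

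Three other statements bear on how the table is used. Section 7.5 says "the dose modifications provided below should be used as a guidance and should be determined as per PI's clinical judgement". Section 7.1.2 says "All adverse events should be graded as per the CTCAE v5.0". Section 3.4.5, after listing raised ALT/AST, skin reactions and neutropenia, says "Monitor patients for signs and symptoms of these events and interrupt Tenalisib for Grade 3 or higher event"; thrombocytopenia is not in that list.

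**The concern.** Neutropenia and thrombocytopenia are low counts, and a higher grade means a lower count. Three of the printed limits say the opposite: they admit normal counts and leave out the lowest ones, against the grade label in the same cell.

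The limits matter because they separate maintaining the dose from withholding it. Section 6.3 requires no protocol laboratory tests. Blood counts are done as standard of care at the investigator's discretion, with study visits every three months. A site holding a local laboratory result and looking for the matching action would compare the count with these printed numbers.

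**Working it through.** There is no sample size or power figure to reproduce. The check is to read each printed inequality as a logical condition and compare it with the condition after the operator is turned round. All counts are in ×10⁹/L.

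**Inputs (section 7.5, Table 2).** The three lines contain four comparisons.

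| Line | Comparison as printed | Literal meaning | Direction |
|---|---|---|---|
| Grade 3 neutropenia, first bound | 1.0 < ANC | ANC > 1.0 | reversed |
| Grade 3 neutropenia, second bound | ANC ≥ 0.5 | ANC ≥ 0.5 | correct |
| Grade 4 neutropenia | 0.5 < ANC | ANC > 0.5 | reversed |
| Grade 4 thrombocytopenia | 20.0 < PLT | PLT > 20.0 | reversed |

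**Step 1: the intended direction, from the table itself.**

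- The febrile neutropenia row uses ANC < 1000/mm³, which is ANC < 1.0. Low counts define the event.
- For patients with a low ANC before therapy, the same row leaves the dose alone while ANC > 0.5. That is the inequality printed for Grade 4 neutropenia, where the action is to withhold. For those patients, one table gives opposite instructions for the same condition.
- The printed Grade 3 line, ANC > 1.0 and ANC ≥ 0.5, reduces to ANC > 1.0, so its second bound does nothing. It forms a range only if the first operator is turned round.
- Considering a platelet transfusion makes sense only for low platelets.

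**Step 2: the conditions after correction.** Grade 3 neutropenia is 0.5 ≤ ANC < 1.0, Grade 4 neutropenia is ANC < 0.5, and Grade 4 thrombocytopenia is PLT < 20.0.

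**Step 3: test counts.**

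| Count | As printed | Corrected |
|---|---|---|
| ANC 0.3 | neither grade | Grade 4 |
| ANC 0.7 | Grade 4 | Grade 3 |
| ANC 4.0 | Grade 3 and Grade 4 | neither grade |
| PLT 10 | not Grade 4 | Grade 4 |
| PLT 250 | Grade 4 | not Grade 4 |

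All five classifications change. For each of the three limits the printed and corrected ranges share no value: ANC > 1.0 against 0.5 ≤ ANC < 1.0, ANC > 0.5 against ANC < 0.5, and PLT > 20.0 against PLT < 20.0. As printed, any ANC above 1.0 falls under both the maintain and the withhold instruction. After correction the two neutropenia ranges adjoin without overlap and agree with the febrile neutropenia row.

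**The case against.** The strongest reply is that this is a typographical slip no hematologist would follow. The column is headed by CTCAE grade, the row names and grade labels are right, and the actions fit the labels. Section 7.5 applies the guidance only to events the investigator judges related to tenalisib, so a patient with an ANC of 4.0 or platelets of 250 has no event and never reaches the table. An ANC of 0.7 would be handled too cautiously rather than too loosely, and an ANC of 0.3 with fever is caught by the correctly printed febrile row. That leaves an afebrile ANC of 0.3 and a platelet count of 10, where the investigator would have to trust an evidently inverted symbol over the grade label. Also, reversing a sign always gives a disjoint range, so the lack of overlap adds little.

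Most of this stands as a limit on the consequence. It does not make the table right, and the two remaining cases are the ones where withholding matters most.

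The section 3.4.5 instruction is only a partial backstop. It does not name thrombocytopenia, and its rule to interrupt at Grade 3 or higher disagrees with Table 2, which maintains the dose at Grade 3 neutropenia. That conflict is a separate matter that correcting the operators would not resolve.

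Two cautions are fair. The documents do not reproduce the CTCAE cut-offs, so the direction is established here but the value of 20.0 for platelets is not. Symbols can also be altered in PDF conversion. However, the same reversal in three cells, beside correctly printed operators in neighboring cells, makes that unlikely.

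**Conclusion.** The concern holds. Three of the four comparisons in these lines of Table 2 are reversed; the lower bound of Grade 3 neutropenia is correct. The table's own febrile neutropenia row establishes the direction for ANC, and the transfusion action establishes it for platelets.

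This should be fixed because the numbers are decision limits in a safety table and describe different patients from the labels beside them. Expected harm is limited by the correct labels, CTCAE grading and the guidance status of the table. Nothing in the sample size, the safety summaries or the progression analysis depends on it.

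The conclusion assumes that the operators on the issued protocol page are as quoted, and it takes no position on whether the three cut-off values match CTCAE v5.0.

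**What to change.** In section 7.5, Table 2, print:

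- Grade 3 neutropenia: 0.5 ≤ ANC < 1.0 ×10⁹/L
- Grade 4 neutropenia: ANC < 0.5 ×10⁹/L
- Grade 4 thrombocytopenia: PLT < 20.0 ×10⁹/L

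Before release, the sponsor's medical lead should check the three cut-offs against CTCAE v5.0, the grading version named in section 7.1.2, and confirm the current operators on the issued page. The change is three operators in one table, made by clarification letter or at the next protocol amendment. It adds no procedures, visits or data.
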